### 6.6.12. Sampling

Refer to the Module on Biospecimen Management in the SPM for detailed instructions for the collection, handling and processing of the samples.

To minimize any development of needle aversion, pain relief by means of a topical local anesthetic may be offered to infants prior to any blood sampling requested by the protocol at the discretion of the investigator and in line with prescribing information.

#### 6.6.12.1. Blood sampling for humoral immunity

Blood samples will be taken during certain study visits as specified in Section [6.5](#) List of Study Procedures.

- A volume of 2.5 mL of whole blood (to provide at least 800 µL of serum) should be drawn from all infants for analysis of humoral response at each pre-defined timepoint. After centrifugation, serum samples should be kept at -20°C/ -4°F or below until shipment. Refer to the SPM for more details on sample storage conditions.
  - Blood sampling for humoral response will not be repeated in case of insufficient volume, at any timepoint except if no blood sample for humoral immunogenicity was collected at the screening visit. In that case an additional blood sample will be taken at Visit 1 that must be taken before vaccination.

**6.6.12.2. Blood sampling for hematology and biochemistry**

[figure not shown]
- A volume of maximum 2.3 mL of whole blood should be drawn from all infants for analysis of the hematology and biochemistry parameters (refer to [Table 12](#)) at each pre-defined timepoint.

Hematology and biochemistry parameters measurement will be performed according to laboratory practices.

If any Grade 1 abnormality with potential clinical relevance (according to investigators judgment, refer to the [glossary of terms](#)) or any  $\geq$  Grade 2 abnormality is detected (refer to [Figure 2](#) and [APPENDIX C](#)):

- at **Screening**, for infants with hematological/biochemical values out of normal range which are expected to be temporary, a re-screening visit may be scheduled during which blood sample collection for hematology/biochemistry will be repeated (maximum one re-screening visit per infant is allowed within the interval planned in [Table 8](#); blood for humoral response will not be re-sampled at the re-screening visit).

*Note: Blood* may be re-sampled for hematology and biochemistry assessment during a re-screening visit (as described above) or during an Unscheduled Visit where there is clinical indication for additional testing.

**Figure 2 Schematic overview of required additional hematology and biochemistry testing during the study****Re-testing at screening**

Note: Blood can be re-sampled for hematology and biochemistry assessment where there is clinical indication for additional testing.

### 6.6.12.3. Nasal swab or other specimen for PCR assay

#### Nasal swab or other specimen for PCR assay collected during assessment visit

Real time assessment of potential RSV-LRTI cases is important for the timely monitoring of safety.

If during passive or active surveillance contact, the investigator/study staff assesses that an infant presents a potential RSV-RTI (refer to Section 9.2), a nasal swab *or* another specimen for assay will be collected during an assessment visit:

- The nasal swab will allow assessing the potential RSV infection by quantitative RT-PCR and respiratory viral panel (RVP) at sponsor laboratory.
- The specimen for local assay will allow assessing the potential RSV infection and RVP at a local routine laboratory, where available. The specimen type will depend on the assay run locally.

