  - Blood samples for **humoral immunogenicity** will be taken from all subjects at Screening and on Day 31, Day 61, and at the visit occurring at the end of the first RSV transmission season.
  - Blood sample for **assessment of mechanism of illness (potential ERD)** will be taken from subjects hospitalized for LRTI (only for RSV-positive subjects using a locally available RSV test).
  - Nasal swab: there will be monthly nasal swab to detect asymptomatic RSV infections during the RSV season and if following active or a passive surveillance contacts, a subject presents symptoms of RTI, a nasal swab will be collected (as well as a sample for local testing i.e., the type of sample to be determined locally [e.g., swab, etc.]) (Refer to the SPM).
- Study visits: Other than the screening visit and assessment visits for active/passive surveillance, there will be 8 study visits except in countries where *Menveo* or Placebo is used as a control where there will be 7 study visits.
  - In countries where *Menveo* is used as a comparator, no administration will be performed at Day 121 and therefore in those countries there will be no Visit 6 and it will be administered at the end of the first RSV season at Visit 7 (refer to [Table 2](#) and [Table 7](#)).
  - In countries where Placebo is used as a control, no vaccine administration will be performed after Visit 3 and therefore in those countries there will be no Visit 6. There will be a Visit 5 and Visit 7 for countries using Placebo and all other study procedures will occur at these visits except vaccination.

- Visit 2 (Day 8), Visit 4 (Day 38), and Visit 8 (no blood sampling for immune response and no vaccine administration) may take place in the subject's home or at the investigators clinical facility as appropriate to the circumstances in the judgment of the investigator.
  - For authorized sites only, Visit 5 (Day 61) and Visit 7 (both with blood sampling) may also take place in the subject's home or at the investigators clinical facility as appropriate to the circumstances in the judgment of the investigator.
- Type of study: self-contained.
- Data collection: electronic Case Report Form (eCRF).
- Safety monitoring: internal safety review committee (iSRC) and IDMC (refer to Section 9.10).
- Surveillance for RSV-RTI, difficulty in breathing, and wheezing episodes.

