**Table 6 Case definitions for data analysis**

Case	At sea level up to 2500 meters elevation	Above 2500 meters elevation
RSV-RTI	Runny nose OR blocked nose OR cough AND Confirmed RSV infection 	Same
RSV-LRTI	History of cough OR difficulty breathing  AND SpO 2 < 95%  , OR RR increase  AND Confirmed RSV infection 	Same but with SpO2 < 92%
severe RSV-LRTI	Meeting the case definition of RSV-LRTI AND SpO 2 < 93%  , OR lower chest wall in-drawing	Same but with SpO2 < 90%
very severe RSV-LRTI	Meeting the case definition of RSV-LRTI AND SpO 2 < 90%  , OR inability to feed, OR failure to respond / unconscious	Same but with SpO2 < 88%
RSV hospitalization	Confirmed RSV infection  AND Hospitalized for acute medical condition 	Same
All-cause LRTI	History of cough OR difficulty breathing  AND SpO 2 < 95%  , OR RR increase 	Same but with SpO2 < 92%

LRTI = lower respiratory tract infections; RR = respiratory rate; RTI = respiratory tract infections; SpO2 = blood oxygen saturation.

Based on [[Modjarrad](#), 2016]

 Based on history reported by parents.

 The lowest value during the course of illness will be used.

 RR increase defined as:

≥ 50/min (2 to 11 months of age)

≥ 40/min (12 months of age or above)

The highest value during the course of the illness will be used.

 RSV infection confirmed on nasal swab positive for RSV A or B by quantitative Reverse Transcription Polymerase Chain Reaction (qRT-PCR).

 RSV sampling and testing is based on medical judgment of medical practitioner or driven by algorithm.

 Hospitalization is defined as a medical decision that the infant requires admission for observation or treatment.

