# These assays will be performed only on enrolled infants and samples from non-enrolled subjects will be discarded.

## 6.7.3. Laboratory assays

Please refer to [APPENDIX A](#) for a detailed description of the assays performed in the study. Please refer to [APPENDIX B](#) for the address of the clinical laboratories for sample analysis.

Determination of a negative RSV exposure status in infants at 6 to 7 months of age will be based on RSV A and/or B neutralizing antibody titers present in serum at screening (before vaccination with the RSV vaccine) based on in-stream baseline serological testing. At birth, newborns do show positive for neutralizing antibodies due to maternal transfer during gestation. The titer of these antibodies declines over time. At the age of 6 to 7 months a cut-off can be defined below which infants are considered to have a negative RSV exposure status. Infants that show neutralizing antibody titers above this cut-off are suspected to have experienced a recent RSV infection. This cut-off will thus allow the discrimination between a negative RSV exposure status versus RSV infected infants before start of vaccination.

The following laboratory assays are planned:

- Functional (neutralizing) antibody titers against RSV-A will be measured by a neutralization assay on serum samples ([Table 10](#)).
- RTI will be assessed by:
  - Quantitative RT-PCR that is able to discriminate RSV-A and RSV-B subtypes ([Table 11](#)).
  - Qualitative multiplex PCR for detection of a panel of viruses ([Table 11](#)).
  - Local RSV assay, and/or local RVP where available ([Table 11](#)) (**Amended 1 August 2019**).

Final confirmation of RSV presence will be obtained through the definitive results from the central test.

These assays will be performed at the investigator's laboratory, at GSK Biologicals' laboratory or at laboratory designated by GSK Biologicals (refer to [Table 10](#) and [Table 11](#)).

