#### **9.2.4. Assessment visit**

The purpose of the assessment visit is to objectively document signs and symptoms by an appropriately qualified person (i.e., medical or nursing), provide medical advice and to take a nasal swab for detection of RSV infection.

- Assessment visits may take place in the subject's home, the investigators clinical facility or a medical facility as appropriate to the circumstances in the judgment of the investigator.
- If the reported symptoms are already of a level of severity that urgent care is indicated, the parent(s)/LAR(s) should be redirected to the proper location to receive this care (e.g., Emergency Room) and an assessment visit could be scheduled to take place there at a suitable time.
- During the assessment visit, the investigator/study staff will evaluate the clinical signs and symptoms of the RTI. Signs and symptoms to be recorded in the eCRF are listed in the SPM.
- Oxygen saturation will be measured by pulse oximetry in room air using standardized equipment in preference.
- Specimen for testing of RSV and RVP at a local routine laboratory will be collected for all the subjects who have symptoms of an RTI.
- Nasal swabs for analysis at sponsor laboratory will be collected for all the subjects who have symptoms of an RTI. Note: all subjects experiencing an RSV-LRTI must be reported as an SAE in an expedited manner (refer to Section 9.4).
- Parent(s)/LAR(s) will be instructed to contact the study staff if the severity of the already existing symptoms increases or if the subject develops difficulty in breathing or wheezing and this may lead to a repeat assessment visit upon the judgment of the investigator.
- During subsequent surveillance contacts after an assessment visit, the status and evolution of the case will be followed until case resolution.
- Each assessment visit will be encoded in the eCRF.

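### Section 6.6.12.3 allows a nasal swab or a local specimen at an assessment visit, while the rest of the protocol requires both and only the nasal swab can confirm RSV in the standardized case definitions

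*Protocol*

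**What the plan says.** The title, subheading and body of Section 6.6.12.3 all use 'or'. The subheading reads: "Nasal swab or other specimen for PCR assay collected during assessment visit". The body reads: "a nasal swab *or* another specimen for assay will be collected during an assessment visit". The two bullets below it show that the samples are not interchangeable. For the first: "The nasal swab will allow assessing the potential RSV infection by quantitative RT-PCR and respiratory viral panel (RVP) at sponsor laboratory". For the second: "The specimen for local assay will allow assessing the potential RSV infection and RVP at a local routine laboratory, where available".

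Other sections require both samples. The sampling schedule in Section 3, like the synopsis, says that for an infant with RTI symptoms "a nasal swab will be collected (as well as a sample for local testing", with the type of local sample chosen locally. Section 9.2.4 has one bullet requiring a local specimen from every symptomatic infant and another stating: "Nasal swabs for analysis at sponsor laboratory will be collected for all the subjects who have symptoms of an RTI". Table 14 lists the nasal swab and the other specimen on separate rows, each for every infant attending an assessment visit.

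The case definitions recognise only one of the two. Table 6, footnote 4, which governs RSV-RTI and RSV-LRTI, reads: "RSV infection confirmed on nasal swab positive for RSV A or B by quantitative Reverse Transcription Polymerase Chain Reaction (qRT-PCR". Severe and very severe RSV-LRTI build on the RSV-LRTI definition and inherit this condition. Section 6.7.3 adds: "Final confirmation of RSV presence will be obtained through the definitive results from the central test". Sections 11.6.4 and 11.10 make quantitative PCR the basis of the primary RTI/LRTI analysis.

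**The concern.** Section 6.6.12.3 is the section named for this sampling, and staff looking up what to collect may well stop there. Read alone, it permits a visit with a local specimen and no central swab. The infant may be RSV-positive on the local test, but the episode does not meet the standardized definition. It then drops out of both numerator and denominator of the very severe RSV-LRTI rate among RSV-infected infants with a negative exposure status. That rate is the quantity on which Section 11.4 bases the sample size and to which Section 11.11 applies the 80% criterion. With so few infections expected, the analysis has little room for avoidable losses.

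**Working it through.** **1. The plan's own figures (Section 11.4).** Expected infections per vaccine group: 50 × 0.5 × 0.2 = 5. The null progression rate is 80%, the assumed rate 10%, and the one-sided type I error 0.05. The rule is at most 1 very severe case of 5.

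- Power = P(X ≤ 1 | n = 5, p = 0.10) = 0.919. This agrees with the stated power of at least 90%.
- Type I error = P(X ≤ 1 | n = 5, p = 0.80) = 0.0067. Allowing 2 of 5 would give 0.058, above 0.05, so 1 is the largest permissible count.

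These figures are correct and are not in dispute.

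**2. Which outcomes need the central swab.**

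| Outcome | Basis for RSV | Lost if sampled only locally? |
|---|---|---|
| RSV-RTI, RSV-LRTI, severe and very severe RSV-LRTI | Table 6, footnote 4; Sections 6.7.3, 11.6.4, 11.10 | Yes, unless a later swab is positive |
| RSV-LRTI as adverse event of special interest | Investigator's judgment with a local test (9.1.5.2, 9.4.4.1) | No |
| RSV hospitalization | Table 6, footnote 5 | Not in this way |
| Monthly IDMC tables | Local results until PCR is available (9.10.3) | Provisionally retained |

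**3. Effect of one lost case.** Section 11.11 asks whether the one-sided 95% upper limit lies below 80%. The exact (Clopper-Pearson) limit U solves P(X ≤ k | n, U) = 0.05.

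| Very severe / confirmed | Upper limit | 80% excluded? |
|---|---|---|
| 2 of 5 | 81.1% | No |
| 1 of 4 (one very severe case lost from 2 of 5) | 75.1% | Yes |
| 2 of 4 (one milder case lost from 2 of 5) | 90.2% | No |
| 1 of 5 | 65.7% | Yes |
| 1 of 4 (one milder case lost from 1 of 5) | 75.1% | Yes |

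Losing a very severe case from 2 of 5 reverses the conclusion. Losing a milder case moves the limit the other way.

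**4. Effect on numbers (illustration only).** The protocol gives no loss rate, so the share lost, f, is an assumption. It is further assumed that every infection is found at an assessment visit and that loss is unrelated to severity. Confirmed infections per group then follow Binomial(50, 0.10 × (1 − f)). Power is averaged over that distribution, using the exact cut-off for each count.

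| f | Expected confirmed | P(at least 5) | Averaged power |
|---|---|---|---|
| 0% | 5.0 | 0.57 | 0.89 |
| 10% | 4.5 | 0.47 | 0.85 |
| 20% | 4.0 | 0.37 | 0.81 |
| 30% | 3.5 | 0.27 | 0.76 |

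Power does not fall steadily with the count. It is 94.8% with 4 confirmed infections (cut-off 1), 72.9% with 3 (cut-off 0) and 81.0% with 2 (cut-off 0). With 1 infection no conclusion is possible.

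**The case against.** The strongest reply is that this is a slip in one section against a rule stated consistently elsewhere. Section 6.6.12.3 itself refers the reader to Section 9.2, where 9.2.4 is explicit. A site sending only a local specimen would breach 9.2.4. Appendix D has a separate field for the central swab, so an omission would be recorded. This stands: any loss depends on a site following 6.6.12.3 literally. It does not remove the contradiction about the sample that defines the case.

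A reader might infer that losses would fall on sicker infants and bias the very severe rate downwards. The documents do not support that. Section 9.2.4 takes the local specimen from all symptomatic infants, not selectively from sicker ones. Section 9.2.5 separately requires a central swab for infants hospitalized with an RTI, and 9.1.5.2 calls for one in RSV-LRTI reported as an adverse event of special interest. Losses could as plausibly fall on milder episodes, which would raise the rate.

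A reader might also infer that every RSV endpoint is affected, or that a case sampled only locally is lost for good. The second table above answers the first. On the second, a repeat assessment visit, a worsening sample or a monthly swab may still catch the infection. These backstops are limited. The monthly swab is in-season only and aimed at symptom-free infants, and the sample at worsening is optional once the previous specimen was RSV-positive (Figure 3, footnote 6).

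Finally, the 10% to 30% loss has no source in the documents. The chance of reaching 5 infections is only 0.57 with no loss at all, and Section 11.4 permits added recruitment. All of this is right, and it is why the figures in step 4 are offered only as an illustration.

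**Conclusion.** The point holds as an internal contradiction with a specific consequence. Section 6.6.12.3 states the wrong rule for the one sample that can confirm RSV under the standardized definitions. An episode sampled only as that section permits is excluded from the RSV-RTI and RSV-LRTI endpoints at every severity grade, and from the progression-rate analysis, unless a later swab is positive.

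How often this would happen cannot be known from the protocol, and the direction of any bias is uncertain. The firm part of the size is the sensitivity to a single case: with about 5 infections per vaccine group, the upper limit can move from 81.1% to 75.1%, across the 80% threshold. The stated sample size and power are unaffected if both samples are always taken. The correction is worth making because the analysis rests on so few infections.

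**What to change.** In the title, subheading and text of Section 6.6.12.3, replace 'or' with 'and', so that every assessment visit takes a nasal swab for the sponsor laboratory plus a specimen for local testing where available. Add one sentence stating that a local specimen does not replace the central nasal swab. This brings the section into line with the synopsis, Section 3, Section 9.2.4 and Table 14.

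The cost is a wording change in the next amendment and a reminder to sites. Both samples are already prescribed in Section 9.2.4 and Table 14, so no new procedure is introduced and the sample size does not change.

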#### Nasal swab collected for PCR assay to detect asymptomatic RSV infections

During RSV season, there will be monthly nasal swabs to detect asymptomatic RSV infections. These nasal swabs will allow assessing the potential RSV infection by quantitative RT-PCR performed centrally at the sponsor laboratory. This swab may be omitted upon investigator discretion if a swab has been taken for a symptomatic episode in the previous 4 weeks.

Refer to the SPM for more details about nasal swab.

### 6.6.13. Surveillance for RSV-RTI and wheezing

Surveillance period for RSV-RTI and wheezing will start at Visit 1 (after Dose 1) until the final visit (Visit 8 [end of the second RSV transmission season]). In order to timely detect RSV-RTI and to ensure cases are timely captured by the study sites, both active and passive surveillance will be conducted as described in Section 9.2. Contacts for active and passive surveillance will be recorded in the eCRF.

If an assessment visit is performed (refer to Section 9.2.4), this visit will be recorded in the eCRF, as well as signs and symptoms. Signs and symptoms to be recorded in the eCRF are listed in the SPM.

At the first vaccination visit (Visit 1 [Day 1]), RTI episode cards will be provided to the subject's parent(s)/LAR(s). At subsequent study visits, new RTI episode card(s) will be distributed as needed. The subject's parent(s)/LAR(s) will record the start date and the end date of the following symptoms: cough, runny nose, blocked nose, difficulty in breathing, or wheezing. The subject's parent(s)/LAR(s) will be instructed to return the completed RTI episode card to the investigator at the next visit or by mail (e-mail or postal mail). The investigator will transcribe the collected information into the eCRF. Any unreturned RTI episode cards will be sought from the subject's parent(s)/LAR(s) through telephone call(s) or any other convenient procedure.

**6.6.14. Check and record concomitant medication/vaccination**

Concomitant medication/vaccination must be checked and recorded in the eCRF as described in Section 7.6.

**6.6.15. Recording of AEs, AEs of special interest and SAEs**

- Refer to Section 9.3 for procedures for the investigator to record AEs, AEs of special interest (RSV-LRTI) and SAEs. Refer to Section 9.4 for guidelines and how to report AEs of special interest and SAE reports to GSK Biologicals.
- The subjects' parent(s)/LAR(s) will be instructed to contact the investigator immediately should the subjects manifest any signs or symptoms they perceive as serious.
- Subjects' parent(s)/LAR(s) will be instructed to contact the investigator/study staff if their child presents symptoms of spontaneous bleeding or easy bruising or if their child develops a rash, within 30 days after either vaccination (Visit 1 and Visit 3), in order to detect any thrombocytopenic petechiae or purpura after each vaccination from Visit 1 [Day 1] to Visit 5 Day 61.
- At each vaccination visit of the RSV investigational vaccine (Visit 1 [Day 1] and Visit 3 [Day 31]), a diary card will be provided to the subject's parent(s)/LAR(s). The subject's parent(s)/LAR(s) will be instructed to measure and record the rectal body temperature (preferred route), any solicited local/general AEs, any unsolicited AEs, and concomitant medications/products/vaccinations on the day of vaccination and 6 subsequent days. The subject's parent(s)/LAR(s) will be instructed to return the completed diary card to the investigator at Visit 2 (Day 8) and Visit 4 (Day 38).

The subject's parent(s)/LAR(s) will record on the same diary card any unsolicited AEs and concomitant medications/products/vaccinations from 7 to 29 days after each vaccination. The subject's parent(s)/LAR(s) will be instructed to return the completed diary card to the investigator at Visit 3 (Day 31) and Visit 5 (Day 61).

The investigator will collect and verify completed diary cards during discussion with the subject's parent(s)/LAR(s) on Visit 2 (Day 8), Visit 3 (Day 31), Visit 4 (Day 38), and Visit 5 (Day 61). The investigator will transcribe the collected information into the eCRF in English.

Any unreturned diary cards will be sought from the subject's parent(s)/LAR(s) through telephone call(s) or any other convenient procedure.

